6.2.3 Adverse Events²

An adverse event (AE) is defined as any untoward medical occurrence in a subject or clinical investigation subject administered a pharmaceutical product at any dose that does not necessarily have to have a causal relationship with this treatment. An AE can, therefore be any unfavorable and unintended sign (including an abnormal laboratory finding, for example), symptom, or disease temporally associated with the use of an investigational product, whether or not considered related to the investigational product. This definition includes intercurrent illnesses or injuries and exacerbation of pre-existing conditions.

An unexpected adverse event is one that is not listed in Package Leaflet or an event that is by nature more specific or more severe than a listed event.

The severity of events reported on the “Adverse Events” CRF will be determined by the investigator as:

Mild: transient with no limitation in normal daily activity.
Moderate: some limitation in normal daily activity.
Severe: unable to perform normal daily activity.

The relationship of the study treatment to an AE will be determined by the investigator based on the following definitions:

1. Not Related

The AE is not related if exposure to the investigational vaccine has not occurred, **or** the occurrence of the AE is not reasonably related in time, **or** the AE is considered unlikely to be related to use of the investigational vaccine, i.e. there are no facts (evidence) or arguments to suggest a causal relationship.

2. Possibly Related

The administration of the investigational vaccine and AE are considered reasonably related in time **and** the AE could be explained by causes other than exposure to the investigational vaccine.

² Adverse Events collected in this study and that are not solicited on a checklist may also be referred to as “unsolicited Adverse Event” in the Clinical Study Report.

3. Probably Related

Exposure to the investigational vaccine and AE are reasonably related in time **and** the investigational vaccine is more likely than other causes to be responsible for the AE, **or** is the most likely cause of the AE.

The relationship of the study treatment to an AE will be determined by the investigator.

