Diary Card Dispensed	X	
Diary Card Collected and/or Reviewed ^d		X
Assess/review Local/Systemic Adverse Events ^e		X
Assess/review AEs and SAEs ^f		X
Concomitant medications ^g	X	X
Study Termination ^h		X

Now reads:

Table 3.3-1: Times and Events Table (2 months through 55 years of age)

Visit Type	Clinic Visit	Telephone or Clinic Visit
Study Day	Day 1	Day 29
Study Visit Window	n/a	-4/+7
ICF/AF ^a	X (Only at 1 st vaccination)	
Exclusion/Inclusion	X	
Medical history	X	
Physical exam/assessment ^b	X	
Demographics	X (Only at 1 st vaccination)	
Study vaccine administered	X	
Immediate hypersensitivity events ^c	X	
Diary Card Dispensed	X	
Diary Card Collected and/or Reviewed ^d		X
Assess/review Local/Systemic Adverse Events ^e		X
Assess/review AEs and SAEs ^f		X
Concomitant medications ^g	X	X
Study Termination ^h		X

Rational for changes: Table was modified to include infant subjects

CHANGE 4 (SECTION 3.3.2)

Previously read:

Adverse events (Not related)

Previously reads:

The AE is not related if exposure to the investigational vaccine has not occurred, or the occurrence of the AE is not reasonably related in time, or the AE is considered unlikely to be related to use of the investigational vaccine, i.e. there are no facts (evidence) or arguments to suggest a causal relationship.

Now reads:

The AE is not related to an investigational vaccine if there is evidence that clearly indicates an alternative explanation. If the subject has not received the vaccine, the timing of the exposure to the vaccine and the onset of the AE are not reasonably related in time, or other facts, evidence or arguments exist that reasonably suggest an alternative explanation, then the AE is not related.

Adverse Events (Possibly related)

Previous reads:

The administration of the investigational vaccine and AE are considered reasonably related in time **and** the AE could be explained by causes other than exposure to the investigational vaccine.

Now reads:

The administration of the investigational vaccine and AE are considered reasonably related in time and the AE could be explained by exposure to the investigational vaccine or by other causes.

Adverse Events (Probably related)

Previously reads:

Exposure to the investigational vaccine and AE are reasonably related in time **and** the investigational vaccine is more likely than other causes to be responsible for the AE, **or** is the most likely cause of the AE.

Now reads:

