Exposure to the investigational vaccine and AE are reasonably related in time and no alternative explanation has been identified.

Rational for changes: All texts have been changed to align with Korean Health Authorities.

CHANGE 5 (section 3.4)

Previously reads:

Expected subject trial participation interval: 29 days

Now reads:

Expected subject trial participation interval: approximately 29 days

The safety will be followed up until the end of surveillance period, and the end date of surveillance will be informed by the sponsor.

Rational for changes: To clarify study participation duration

Novartis

Document Approval Certificate /

PPD

The individuals listed have approved this document for implementation using an electronic signature in the Atlas EDMS. / PPD

UserName: PPD

Title: Cluster Physician

Date: Monday, 01 June 2015, 10:41 GMT

Meaning: As an approver, I agree with the content and format of this document.

=====

This signature certificate is only valid when accompanied by all the pages of the document. /

PPD

CLINICAL STUDY PROTOCOL V59_62

**A Multicenter Post Marketing Surveillance Study to Monitor the Safety of GSK
Meningococcal ACWY Conjugate Vaccine (MenACWY-CRM) Administered
According to the Prescribing Information to Healthy Subjects from 2 months to 55
Years of Age in the Republic of South Korea**

Amendment Number 4

Revised Protocol version 5.0 issued on 25 August 2015

The present amendment reflects changes to the Protocol version 4.0

Issued on 12 May 15

Property of GSK

Confidential

**May not be used, divulged, published or otherwise disclosed without written
consent of GSK.**

DESCRIPTION OF CHANGE(S) AND RATIONALE:

CHANGE 1

The entire document has been revised to ensure all instances where Novartis is mentioned are replaced with GSK.

Rationale for Change:

Due to change of Marketing Authorization Holder from Novartis Vaccines to GSK Vaccines, the document has been revised to change name of Sponsor.

Novartis

Document Approval Certificate /

PPD

The individuals listed have approved this document for implementation using an electronic signature in the Atlas EDMS. / PPD

UserName: PPD

Title: Cluster Physician

Date: Thursday, 27 August 2015, 22:00 GMT

Meaning: As an approver, I agree with the content and format of this document.

=====

This signature certificate is only valid when accompanied by all the pages of the document. /

PPD

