2.1 Safety Set

Table 2.1.1 Summary of AE

Safety set	No. subjects with AE n (%)	95% CI† for the percentage of subjects with AE (Lower , Upper)	No. AEs n	No. subjects with ADR n (%)	95% CI† for t percentage o subjects with A (Lower , Upp
Solicited AE (2-23 months)					
Local AE					
Systemic AE					
Solicited AE (2-5 years)					
Local AE					
Systemic AE					
Solicited AE (≥ 6 years)					
Local AE					
Systemic AE					

Safety set	No. subjects with AE n (%)	95% CI† for the percentage of subjects with AE (Lower ,Upper)	No. AEs n	No. subjects with ADR n (%)	95% CI† for the percentage of subjects with ADR (Lower ,Upper)	No. ADR n	Total n (%)
Unsolicited AE							
SAE							
MAAE							
Death							
Total							

† 95% CI will be calculated using the normal approximation.

* Day 1-7: Solicited AE, Unsolicited AE

* Day 1-29: SAE, Death

* Day 8-29: MAAE

Table 2.1.2 Summary of AE by Age (month, year)

Safety Set	No. subjects with AE	No. AEs	Total	p-value
	n (%)	n	n (%)	
2-23 months				X ² -test or Exact test
2-10				
2-5				
6-10				
11-18				
19-34				
35-55				
> 55				
Total				

Table 2.1.3 Summary of AE by Age (month, year)

Safety Set	No. subjects with AE	No. AEs	Total	p-value
	n (%)	n	n (%)	
Solicited AE				X ² -test or Exact test
2-23 months				
2-10				
2-5				
6-10				
11-18				
19-34				
35-55				
> 55				
Solicited Local AE				X ² -test or Exact test
2-23 months				
2-10				
2-5				
6-10				
11-18				
19-34				

Safety Set	No. subjects with AE n (%)	No. AEs n	Total n (%)	p-value
35-55 > 55				
Solicited Systemic AE 2-23 months 2-10 2-5 6-10 11-18 19-34 35-55 ≥56				X ² -test or Exact test
Unsolicited AE 2-23 months 2-10 2-5 6-10 11-18 19-34 35-55 ≥56				X ² -test or Exact test
SAE 2-23 months 2-10 2-5 6-10 11-18 19-34 35-55 ≥56				X ² -test or Exact test
MAAE 2-23 months 2-10 2-5				X ² -test or Exact test

Safety Set	No. subjects with AE n (%)	No. AEs n	Total n (%)	p-value
6-10				
11-18				
19-34				
35-55				
≥56				
ADR				
2-23 months				
2-10				
2-5				
6-10				X ² -test or Exact test
11-18				
19-34				
35-55				
≥56				
Death				
2-23 months				
2-10				
2-5				
6-10				X ² -test or Exact test
11-18				
19-34				
35-55				
≥56				

Table 2.1.4 Summary of AE by Children group

Safety Set	No. subjects with AE n (%)	No. AEs n	Total n (%)	p-value
< 18 years				
≥ 18 years				X ² -test or Exact test
Total				

Table 2.1.5 Summary of AE by Gender

Safety Set	No. subjects with AE n (%)	No. AEs n	Total n (%)	p-value

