6.2.1 Adverse Events by Baseline Characteristics

AE[†]s (as described below) will be reported (n %) for the following baseline characteristics in the safety set and safety per protocol set :

- Age group (2-23 months, 2-10, 11-18, 19-34, 35-55, 55-64)
- Children group (<18, ≥18)
- Gender (male, female)
- Past diagnosis (yes, no)

	CONFIDENTIAL :	Last Update Date
	THIS DOCUMENT AND INFORMATION CONTAINED HEREIN IS PROPRIETARY TO COMPANY AND IS NOT TO BE DISCLOSED WITHOUT THE WRITTEN PERMISSION OF COMPANY.	20-APR-2018
STATISTICAL ANALYSIS PLAN(V6.0)		

- Temperature location (axillary, oral, rectal, ear)
- Administration site (left deltoid, right deltoid, left thigh, right thigh, other)
- Concomitant medication (yes, no)
- Kidney disorder (yes, no)
- Liver disorder (yes, no)
- Pregnancy (yes, no)
- Number of previous Menveo (0, 1, 2, 3)
- Study vaccination number (1, 2, 3, 4)

The n(%) of AEs[†] and its 95% confidence interval will be calculated using the normal approximation and analyzed using χ^2 - test. If more than 20% of expected frequencies of the cell counts are less than 5, Fisher’s exact test will be used instead of the chi-square test.

† AE : AE includes solicited and unsolicited AE (DAY 1-7), medically attended AE (DAY 1-29) and SAE (DAY 1-29).

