6.2.3 Analysis of Unsolicited AE

All unsolicited AEs and MAAE recorded in the CRF will be mapped to preferred terms using the most recent MedDRA dictionary and classified by System organ class (SOC) and Preferred Terms (PT). Under the classification standard of MedDRA terms, and all AEs excluding the AEs whose causal relation with the study medication is ‘Not Related’ shall be treated as AEs whose causal relation cannot be excluded {hereafter “Adverse Drug Reaction(ADR)”}.

- ① The frequency and percentage of unsolicited AE (Day 1-7) and MAAE (Day 1-29) according to the expected, serious, severity, frequency, action taken, outcome, relationship to MenACWY-CRM regarding occurred AE will be calculated.
- ② The frequency of unsolicited AEs (Day 1-7) and MAAE (Day 1-29) will be classified into the preferred terms according to the expected, serious, severity, frequency, action taken, outcome, relationship to MenACWY-CRM.
- ③ The number of subjects and percentage of SAE/Serious ADR (SADR), unexpected AE/ADR,

	CONFIDENTIAL :	Last Update Date
	THIS DOCUMENT AND INFORMATION CONTAINED HEREIN IS PROPRIETARY TO COMPANY AND IS NOT TO BE DISCLOSED WITHOUT THE WRITTEN PERMISSION OF COMPANY.	20-APR-2018
STATISTICAL ANALYSIS PLAN(V6.0)		

MAAE/ADR, unsolicited AE/ADR and continuous solicited AE/ADR will be calculated according to the preferred terms. And the number of subjects and percentage by study vaccination number of SAE/Serious ADR (SADR), unexpected AE/ADR, MAAE/ADR, unsolicited AE/ADR and continuous solicited AE/ADR will be calculated according to the preferred terms in infants 2 to 23 months.

- ④ For subjects excluded from safety per protocol set[†], the number of subjects and the percentage of SAE/Serious ADR (SADR), unexpected AE/ADR, MAAE/ADR, unsolicited AE/ADR and continuous solicited AE/ADR will be calculated according to the preferred terms. And the number of subjects and percentage by study vaccination number of SAE/Serious ADR (SADR), unexpected AE/ADR, MAAE/ADR, unsolicited AE/ADR and continuous solicited AE/ADR will be calculated according to the preferred terms in infants 2 to 23 months.

[†] Subject excluded from safety per protocol set: Except for subjects who didn't receive study vaccination and follow-up failure.

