7.4 Additional Analyses for DDS (Data Disclosure Shell)

- Frequency and percentage by Age group (2-23 months, 2-10, 11-18, 19-64)
- Frequency and percentage by study termination and reason not completed
- Incidence proportion and the number of Non-SAE
- The number of death resulting from AE (frequency and percentage)
- Incidence proportion and number according to the preferred terms of Non-SAE (frequency and percentage)

7.5 Additional Analyses for AE in the Local Product Label (Unsolicited AE Day 1-29)

- Preferred terms of Serious AE/ADR, unexpected AE/ADR will be presented respectively according to the proportion.

	CONFIDENTIAL :	Last Update Date
	THIS DOCUMENT AND INFORMATION CONTAINED HEREIN IS PROPRIETARY TO COMPANY AND IS NOT TO BE DISCLOSED WITHOUT THE WRITTEN PERMISSION OF COMPANY.	20-APR-2018
STATISTICAL ANALYSIS PLAN(V6.0)		

8. Notes

- Each statistical analysis will be carried out with SAS Software version 9.4 or more recent version.
- In the descriptive statistics, mean, SD, minimum, median, and maximum will be calculated for continuous variables, and frequency and percentage for categorical variables.
- Data including sign of inequality such as “ ≥ 20 ”, “ > 20 ” will be excluded from analysis.
- All test statistics will be the results of two-sided tests with the statistical significant level of 0.05.
- The followings shall be included only in re-examination report:
 - Analysis by type of concomitant medications
 - Item ② of paragraph 6.2.3
 - Estimation of 95% confidence interval for incidence proportion of AEs by background factors
 - Paragraph 6.3, 6.4

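### Causality categories changed mid-study at Amendment 3, yet the SAP pools ADRs across both definitions and compares them by age, which is associated with the definition in force

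*Protocol*

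**What the plan says.** **Original definitions (Protocol 6.2.3).** An AE was Not related if the vaccine had not been given, if the timing was unreasonable, or if a link was thought unlikely. Unlikely was explained as "there are no facts (evidence) or arguments to suggest a causal relationship". Possibly related covered a well-timed event where the "AE could be explained by causes other than exposure to the investigational vaccine".

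**Definitions from Amendment 3, Change 4.** The text now opens with "The AE is not related to an investigational vaccine if there is evidence that clearly indicates an alternative explanation". Its next sentence also allows Not related when the vaccine was not received, when the timing is unreasonable, or when other facts or arguments reasonably suggest an alternative. Probably related becomes "Exposure to the investigational vaccine and AE are reasonably related in time and no alternative explanation has been identified".

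**ADR definition (SAP V6.0, 6.2.3; same in V4.0 and V5.0).** All AEs except those judged Not Related "shall be treated as AEs whose causal relation cannot be excluded" and are called ADRs. The rule does not refer to protocol version. No SAP version splits ADR output by period, plans to re-assess earlier events, or mentions the change.

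**Outputs that use it.** In SAP V4.0, Appendix 1:
- Tables 2.1.1 and 2.2.1 give ADR percentages with 95% intervals.
- Tables 2.1.3 and 2.2.3 give ADRs by age group, from 2-23 months upward, with a chi-square or exact p-value.
- Sections 7 to 9 give serious, unexpected and medically attended ADRs by age column.

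The revision logs of V5.0 and V6.0 record no removal of these tables. V6.0 adds section 6.4, which sets serious and unexpected AE/ADR terms against the local product label. SAP section 8 states: "All test statistics will be the results of two-sided tests with the statistical significant level of 0.05".

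**The concern.** An ADR here is defined entirely by one investigator judgement, and the rule for that judgement changed during enrolment. A pooled ADR or serious-ADR percentage therefore mixes two definitions in a proportion set by accrual. That is awkward for a single summary figure and worse for a comparison across age groups, because eligibility opened in calendar order: 11-55 years at the start, 2-10 years with Amendment 1 in 2013, infants with Amendment 2 in October 2014. Age groups are likely to differ in the share of their events judged under each definition. A difference in ADRs between infants and older subjects could then come from the definition alone, and the planned p-value would not reveal it.

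**Working it through.** **1. What can move, and which way.**

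| Well-timed AE | Original text | Amendment 3 text | Effect on ADR count |
|---|---|---|---|
| Nothing suggests the vaccine, nothing suggests another cause | Could be Not related | Probably related | Into ADR |
| Another cause could explain it | Could be Possibly related | May be Not related | Out of ADR |
| Vaccine and another cause both plausible | Possibly related | Possibly related | None |

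The net change in the ADR share of AEs is inflow minus outflow. The documents give neither.

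**2. How age and definition are associated.** I used the approval dates of the amendments, an end at 22 May 2018 (SAP 2.1), and the 6-year enrolment period (Protocol 3.2), which implies a start near 22 May 2012. Uniform accrual is an assumption. Share of each enrolment window before 1 June 2015:
- 11-55 years: 1,105 / 2,191 days = 50% (43% if counted from 6 March 2013, the date on SAP V1.0)
- 2-10 years, from 3 June 2013: 728 / 1,814 = 40%
- 2-23 months, from 28 October 2014: 216 / 1,302 = 17%

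**3. What that could do to the comparison.** The plan gives no ADR or causality rate to reproduce. Its only usable figures are the evaluable cohorts, 600 infants and 3,000 older subjects (SAP 2.2; 3,600 x 1.10 = 3,960, the stated enrolment).

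Let a be the proportion of subjects with a causality-assessed AE, equal at all ages, and q the probability that such an AE is called an ADR. With a share f under the old definition:

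ADR proportion = a x [f x q(old) + (1 - f) x q(new)]

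For a = 10%, q from 0.2 to 0.4, f = 0.166 in infants and 0.504 in older subjects:
- infants: 0.10 x (0.166 x 0.2 + 0.834 x 0.4) = 3.7%
- older: 0.10 x (0.504 x 0.2 + 0.496 x 0.4) = 3.0%
- ratio 1.23, with no true age effect

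Rejection rates at two-sided 0.05, from 20,000 simulated trials per scenario (a = 10%):

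| q old to new | Infants | Older | Ratio | Pooled chi-square | Cochran-Mantel-Haenszel by definition |
|---|---|---|---|---|---|
| 0.2 to 0.4 | 3.7% | 3.0% | 1.23 | 15.4% | 5.0% |
| 0.2 to 0.6 | 5.3% | 4.0% | 1.34 | 33.1% | 5.1% |
| 0.4 to 0.3 | 3.2% | 3.5% | 0.90 | 5.8% | 5.0% |
| 0.4 to 0.4 | 4.0% | 4.0% | 1.00 | 5.1% | 5.2% |

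**4. Sensitivity.** With a from 5% to 20%, the pooled test rejects 5% to 57% of the time. If no infant falls under the old definition, the range is 5% to 87%. If the older share is 35%, it is 5% to 21%. If both cohorts have the same share, it is 5%, as it should be. The stratified test stays at 4.6% to 5.2% in every scenario in which it was run.

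The calculation uses two groups and applies the 11-55 share to all older subjects; the planned table tests all age groups together. It shows the mechanism and does not forecast a result.

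**The case against.** The strongest reply is that nothing central is touched. The four endpoints (SAP 4.1) are all-causality counts, Protocol 7.1 calls every analysis descriptive, and the V4.0 shells also show Not, Possibly and Probably related separately by age. The ADR-by-age p-value is visible only in the V4.0 appendix; V6.0 6.2.1 describes tests for AEs, and the V6.0 appendix is not among the documents. All of this is correct and limits the point to causality-filtered outputs. It does not remove it: the shells show relationship by age but not by period, a 0.05 test is still specified, and V6.0 6.4 uses ADRs against the label.

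Three stronger readings are tempting, and the documents do not support them.
- **That Not related now needs clear evidence of another cause.** The sentence after the opening one also accepts facts or arguments that reasonably suggest an alternative, and keeps the exits for timing and non-receipt.
- **That the change can only add ADRs, and so biases infants upward.** The old Possibly related category could hold events that are now Not related, so the net shift could be positive, zero or negative.
- **That almost all infants were judged under the new text.** They were eligible for about seven months (216 days) before approval of the change, and neither accrual by period nor site implementation dates are given.

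**Conclusion.** The point stands in a limited form. Two causality definitions were in force one after the other, both feed one ADR variable, and age is associated with which one applied. The pooled ADR-by-age contrast is therefore confounded, and pooled ADR and serious-ADR percentages mix two definitions.

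Size and direction cannot be determined from the documents. The illustrations depend on assumed AE and ADR rates, uniform accrual, and a switch on the approval date. They range from negligible to a false-positive rate several times nominal. The point also assumes that the V4.0 ADR-by-age tables were carried forward, which the revision logs suggest but do not prove. Total AE, MAAE and SAE counts are not affected. The result to expect without a fix is a misleading descriptive contrast and p-value, not a failed primary analysis.

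**What to change.** In SAP 6.2.3:
1. Define a period variable: before or after Amendment 3 took effect, by site where that date is known, otherwise by its approval date. Use vaccination date to place subjects, since those without an AE need a period too, and AE onset date to check events near the boundary. Both dates are already collected (Protocol 3.3.1). State how infants followed after doses in both periods are handled.
2. Tabulate ADRs and serious ADRs by period beside the pooled figure.
3. Replace the unstratified ADR-by-age p-value with a comparison stratified by period, for example Cochran-Mantel-Haenszel. Stratifying keeps the earlier data on older subjects, which restricting to the later period would discard.
4. Describe the definition change in the report, including where section 6.4 results are given.

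The cost is one derived variable, an extra table and smaller numbers per stratum. No date of causality assessment is listed among the survey items, so vaccination or onset date is only a proxy for the definition the investigator actually applied. Re-assessing earlier events under one definition would remove that limitation, at greater cost.

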STATISTICAL ANALYSIS PLAN(V1.0)		

8. Notes	16
Appendix1	17

	CONFIDENTIAL :	Last Update Date
	THIS DOCUMENT AND INFORMATION CONTAINED HEREIN IS PROPRIETARY TO COMPANY AND IS NOT TO BE DISCLOSED WITHOUT THE WRITTEN PERMISSION OF COMPANY.	06-MAR-2013
STATISTICAL ANALYSIS PLAN(V1.0)		

1. Study Objective

The primary objective of the study is to monitor the safety of a single dose of MenACWY-CRM vaccine in subjects from 11 to 55 years of age, as evaluated by:

1. Local and systemic solicited reactions reported from study Day 1(day of vaccination) through study Day 7 post-vaccination
2. All unsolicited Adverse Events (AEs) reported from study Day 1(day of vaccination) through study Day 7 post-vaccination
3. Medically attended Adverse Events reported from study Day 1 to study termination (Day 29/early termination)
4. All Serious Adverse Events (SAEs) reported from study Day 1 to study termination (Day 29/early termination)

2. Study Method and Study Period

